### **Data Analysis**

Statistical analysis will be performed by the Oculoplastic Research Laboratory research fellow. A paired t-test will be used to analyze the difference in palpebral fissure height, ocular surface and tearing. 34 subjects will be required to perform perimetric statistics.

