## 5) Procedures Involved\*

*Patients coming to the oculoplastic clinic who qualify for the study based on inclusion and exclusion criteria (With upper lid retraction or asymmetry>1mm) will have the study explained to them by a research study member and they can ask questions. They will receive information on risks and benefits to research participation. For interim analysis of futility, we will do the study with BT eye drops on first 10 patients and then evaluate the results to see if there are any significant effects. If clinically significant effects are seen, then 34 patients totally (17 in BT vs 17 in saline) are included. After a written consent is obtained, External Photographs will be taken by a standard camera in standardized room light. Eyelid measurements will be done including MRD1, MRD2, PF height with the eyes in the primary position. Tear meniscus height, Schirmer I test with anesthesia and ocular staining with fluorescein will be evaluated for all patients recruited before and after eye drops are installed by the PI or resident in the clinic in the eye with greater palpebral fissure height (one eye). In each visit all these data will be obtained again. The subjects will be allocated to the treatment based on the randomization sheet provided by the biostatics department that is handed to [name], Surgical Coordinator on the 4th who will inform the PI of the patient's number. After the PI sees the patient, she will inform the resident in the clinic. The resident or the fellow in the clinic will be asked to provide the PI with the eye drop (botulinum toxin A or saline in 1 cc syringes without needles) while not informing of the contents. The research team([name], [name], [name], [name]), also blinded to the study will gather the data and take the necessary photos (double Blinded).*

*Potential toxicity or life-threatening toxicity with topical botulinum toxin is unlikely.*

*Pressure on the lacrimal sac by the patients for 2 minutes will be done to minimize systemic absorption.*

*Patients will be provided a phone number to call if any complications occur.*

*BOTOX®, JEUVEAU, XEOMIN, and DYSPORT are Crystalline preparations of BT type A, FDA approved drugs for many indications including periocular wrinkles. Saline eye drops will be also used as placebo.*

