## **Number of Subjects**

10 Patient are recruited for interim analysis of futility. If significant, then 17 patients in each group (34 total) based on power calculations for alpha of 0.05 and power of 80% per the biostatistics department.

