## **Study Timelines**

Recruitment will occur for 1 year. After interim analysis, the study will end once 34 patients are recruited. The study length for the patient is expected to be at least 3 months, with the recruitment/baseline visit and follow up visits at 3 days, 1 week, 2 weeks, 1 and 3 months from the first visit, for a total of 6 visits. The study is expected to last about 1 year from the time of IRB approval to completion of all study activities, including analysis of identifiable data.

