## Procedures Involved

**We anticipate that the procedures listed below will take about 30 to 40 minutes per patient. Each patient will have a complete ophthalmologic exam. Except as noted, the procedures below are not considered standard of care and are being conducted for the study alone.**

- A. Part 1: Pre-treatment data collection
  - External photographs, MRD1, MRD2, palpebral fissure height, tear meniscus height, Schirmer I test with anesthesia and ocular staining with fluorescein will be recorded.
- B. Part 2: Botulinum toxin or Placebo topical application
  - Subjects will be randomized to receive either 15 units of botulinum toxin A (BOTOX), incobotulinum toxin A (XEOMIN), prabotulinum toxin A (JEUVEA), the equivalent of 45 units of abobotulinum toxin A (DYSPORT) or balanced saline placebo in one eye after 10 patients are included for the interim analysis with BT eye drops topically on the surface of the eye
  - Then based on the randomization results, the examiner will apply botulinum eye drops or saline to the one of the subject's eyes.
- C. Part 3: Post-treatment data collection
  - Subjects will come back in 3 days, 1 week, 2 weeks, 1 & 3 months after they receive the treatment or control.
  - At each visit, subjects will have the measurements above again.
- D. Part 4: Data analysis
  - Data will be recorded and stored in a secure Microsoft Office Excel (Microsoft Corporation, Redmond, WA, U.S.A.) spreadsheet. Data will be graphically analyzed and represented with Adobe Photoshop (Adobe, Inc., San Jose, CA, U.S.A.).
  - Data assessed will involve assessing pre- and post-treatment MRD1 and MRD2, investigator-assessed measurements of ocular surface and tearing.
  - User performing analysis will be blinded to which eye received study drug.

Follow-up outside of the patient's next routine clinic visit will be needed for 3 days, 1 week, 2 weeks and 1 & 3 months. Patients who do have symptoms concerning any post-procedural complications will be instructed to notify study staff immediately. A phone number will be provided.

Outcomes Measures:

Primary outcome:

Outcome Measure Title: Change in palpebral fissure height

Outcome Measure Description: Palpebral fissure height will be calculated from the sum of marginal reflex distance 1 and 2 measured by the researcher.

Outcome Measure Timeframe: Baseline, day 3, 7, 14, 30 & day 90.

Secondary outcomes:

Outcome Measure Title: Change in eye ocular surface and tearing

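### The only test named is a paired t-test, but separate patients are randomised to botulinum toxin or saline, so no drug-versus-placebo comparison is specified

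*Combined protocol and SAP*

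**What the plan says.** **Analysis.** The Data Analysis section states: "A paired t-test will be used to analyze the difference in palpebral fissure height, ocular surface and tearing". It does not say which two measurements form a pair, and no other test appears in the document. Part 4 of the later Procedures Involved section points to a before/after reading: "Data assessed will involve assessing pre- and post-treatment MRD1 and MRD2".

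**Design.** Section 5 runs two stages. First, "we will do the study with BT eye drops on first 10 patients". If the effect looks clinically significant, "then 34 patients totally (17 in BT vs 17 in saline) are included". Subjects, not eyes, are allocated from a randomisation sheet. Each receives BT or saline, double-blind, "in the eye with greater palpebral fissure height (one eye" only). No matching of BT patients to saline patients is described, and nobody receives both.

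**Size and timing.** Number of Subjects gives "17 patients in each group (34 total) based on power calculations for alpha of 0.05 and power of 80" per cent. Study Timelines adds: "After interim analysis, the study will end once 34 patients are recruited". The primary outcome is change in palpebral fissure height, with the time frame "Baseline, day 3, 7, 14, 30 & day 90". That is five post-treatment visits, none of them named as primary.

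**The concern.** Randomisation, placebo and blinding exist so that BT can be compared with saline. The named test does not make that comparison. It asks whether a patient's eye changed, or differs from the fellow eye, and neither question estimates BT minus saline.

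This matters more than usual here because of how the study eye is picked. The eye with the greater measured height is treated, and entry requires lid retraction or asymmetry of more than 1 mm. An eye chosen for a high reading tends to read lower next time, which is the direction of the trial's hypothesis. Placebo response or drift in the measurements could add to this. The saline arm removes these effects only if the arms are compared directly. Finding that BT was significant and saline was not would not be such a comparison.

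**Working it through.** **1. Does the test match the design?**

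| Stage | Patients | Paired t-test suitable? |
|---|---|---|
| First 10 | All receive BT | Yes, for before/after change; there is no control |
| Randomised | 17 BT and 17 saline, unmatched, one eye each | Within an arm only; it cannot test BT against saline |

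Both possible pairings (before/after, treated/fellow eye) are within-patient, so the conclusion does not depend on which was meant.

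**2. The plan's own figure.** The 17 per group cannot be reproduced, because no effect size, SD or test is given for the power calculation. Solving backwards for a two-sample t-test (two-sided 0.05, noncentral t with 17 + 17 − 2 = 32 df and noncentrality d × √(17/2)), power is 80% at d = 0.99 SD. At an assumed d = 1.0, 17 per arm gives 80.7% and 16 gives 78.1%.

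**3. An inert drop with a shift common to both arms (shift assumed).** The paired test has 16 df and noncentrality d × √17. Let p be the chance that it is significant in the BT arm. The chance that BT is significant and saline is not is p(1 − p).

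| Shift (SD of change) | d × √17 | p | p(1 − p) |
|---|---|---|---|
| 0.2 | 0.82 | 0.121 | 0.107 |
| 0.3 | 1.24 | 0.214 | 0.168 |
| 0.5 | 2.06 | 0.491 | 0.250 |

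**4. How much of a shift comes from choosing the larger eye?** Let e be the measurement-error SD per eye and s the SD of the true difference between a patient's two eyes. The measured difference has SD m = √(s² + 2e²). The expected spurious fall in the chosen eye is (e²/m) × k. Here k = 0.798 with no asymmetry threshold, and k is the normal hazard at 1/m if measured asymmetry must exceed 1 mm.

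- Smallest case: e = 0.3, s = 1.5, no threshold. m = √(2.25 + 0.18) = 1.56, so the fall is (0.09/1.56) × 0.798 = 0.05 mm.
- Largest case without a threshold: e = 0.7, s = 1.0. m = √(1 + 0.98) = 1.41, so the fall is (0.49/1.41) × 0.798 = 0.28 mm.
- The same case with the threshold: k = 1.30, so the fall is (0.49/1.41) × 1.30 = 0.45 mm.

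Simulation used arms of 17, 8,000 per scenario and 36 scenarios: e = 0.3, 0.5 or 0.7 mm; s = 1.0 or 1.5 mm; extra variation at follow-up of SD 0, 0.5 or 1.0 mm; threshold absent or present. All of these inputs are assumptions.

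| Test, inert drop | No threshold | >1 mm threshold | Nominal |
|---|---|---|---|
| Paired, BT arm, false decrease | 4–21% | 4–46% | 2.5% |
| Two-sample on change, BT against saline (both threshold settings combined) | 4–6% | 4–6% | 5% |

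**5. Status of the first 10.** If the first 10 counted inside the 34 and the totals stayed at 17 and 17, the randomised comparison would be 17 − 10 = 7 BT against 17 saline. Power would be 80% only at 1.32 SD, and 56% at 0.99 SD.

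**The case against.** The strongest reply is that this is a drafting gap. Seventeen per group, set by the biostatistics department, is what a two-sample t-test needs at a difference of 1.0 SD, so a comparison of arms may well have been intended. Nothing in the document declares success on BT being significant while saline is not, and a paired test does suit the first 10 patients. All of this is fair, and intent to rely on separate within-arm tests is not shown. But an intended test is not a specified one, and the one test that is specified cannot be applied across unmatched arms.

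The sizes are also open to challenge. No SD or measurement error is in the documents. The 46% is one corner: largest error, smallest between-eye spread, no extra follow-up variation and the threshold applied to every patient. If the assumed spread of 1.0 mm is read as an SD per eye rather than of the difference, that corner falls to about 27–28%. Patients may also enter on lid retraction alone, so the range without a threshold, 4–21%, is the safer one to quote. Its lower end is only slightly above nominal. These points limit the figures but leave the mismatch untouched.

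Finally, the 34 read most naturally as all randomised, so the 7-against-17 case is contingent. No claim is made that the sample size is wrong.

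**Conclusion.** The concern holds and should be corrected before the randomised data are analysed. The mismatch follows from the text alone: patients are randomised in parallel groups, the only named test is within-patient, and no test of BT against saline is specified for any of the three aims.

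How badly a within-arm result would mislead depends on assumed quantities. A shared shift of 0.2 to 0.5 SD makes the BT-arm paired test significant in 12% to 49% of trials of an inert drop. Selection of the larger eye alone gives a false decrease in about 4–21% of trials without an asymmetry threshold, against a nominal 2.5%, and more with one. A between-arm test keeps its error rate in the same scenarios.

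**What to change.** In Data Analysis, replace the paired t-test as the primary analysis with:

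- a BT-minus-saline comparison of palpebral fissure height, adjusted for baseline height (ANCOVA, or a mixed model giving the same contrast), two-sided 0.05, with a 95% confidence interval;
- at one visit named before the randomised stage begins, with the other visits secondary;
- in randomised patients only, with the first 10 BT patients reported separately and not pooled.

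A two-sample t-test on change would also be valid. With equal variances at the two visits, ANCOVA has (1 + r)/2 times the variance of the change-score analysis, which is 0.75 to 0.90 for an assumed baseline–follow-up correlation r of 0.5 to 0.8. Compare Schirmer between arms in the same way, and staining between arms by a method suited to the score, such as a rank-based or ordinal one. Paired t-tests may stay as descriptive within-arm results.

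In Number of Subjects, state the difference, SD and test behind 17 per arm, noting that a two-sample t-test reaches 80% power only at about 0.99 SD. State also whether the first 10 are outside the 34.

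The cost is wording. Baseline height is already recorded, and no visit or measurement is added. No extra patients are needed if all 34 are randomised. If the first 10 were meant to count, keeping 17 against 17 randomised takes 10 more.

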## **6) Risks to Subjects\***

The primary risks to the subjects are adverse reactions to the medication. These risks are explained to patients prior to their arrival to the oculoplastic clinic. Previously described potential adverse reactions when injecting the periocular area are dull and transient headaches with malaise, Ptosis. Severe reactions seen in injections of BT in non-periocular areas such as anaphylaxis, soft-tissue edema and dyspnea are rare in occurrence. (28) Injection of BT in neck: Hoarseness and dysphagia). (28)

All are reversible side effects. (28)

Subjects may have mild ptosis in due to botulinum eye drop but it will eventually improve. Also, the drop can be used in the opposite eye to give symmetry.

Potential psychosocial risks to subjects include time taken from their day to undergo tests, potentially missing work, and anxiety or discomfort from the eye drop instillation process. This study is not collecting sensitive information, thus no potential risk to reputation or legal risks should occur.

Subjects will be instructed to call immediately for an appointment if they notice a change in their vision, eye redness, or the development of pain in either eye. Care will be taken by all study members to prevent the occurrence of any adverse events.

There are no well-controlled studies of BT-A eye drops in pregnant women, and the risks to the fetus or embryo are unknown/unforeseen. One prior publication reported abortion or fetal malformations which have been observed in rabbits after injection (29) however, another larger prospective study found no increased risk of malformations associate with BT-A for chronic migraine during pregnancy in 45 patients (30). No studies have been performed evaluating topical BT ophthalmic solution. BT is classified as US FDA pregnancy category C. (29)

- US FDA pregnancy category C: Animal reproduction studies have shown an adverse effect on the fetus and there are no adequate and well-controlled studies in humans, but potential benefits may warrant use of the drug in pregnant women despite potential risks.

Participants will be informed of the above information and reserve the right to decline participation in the study. We will not be following pregnancy outcomes.

Unanticipated problems or complications will be reported to the IRB according to posted guidelines.

Risks of the study are listed above and will be minimized by the following:

- Study will be discontinued if subjects experience any negative effect from the medication
- Patients with a known sensitivity or history of adverse reaction to BT or similar medications will be excluded from the study

As with any study, there is a risk of confidentiality breach. The research members will assign each patient a specific ID number and place this information on a separate spreadsheet. No names will be used in the forms. Presentations and publications will not identify individual patients.

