#### Adverse Events and Serious Adverse Events

Treatment-emergent adverse events, defined as any event, not present prior to the initiation of the drug treatment or any event already present that worsens in either intensity or frequency following exposure to the drug treatment, will be monitored and reported throughout the study. Treatment emergent adverse scale will be graded as the following:

- Mild: Transient or mild discomfort (<48 hours) to the subject; no medical intervention/therapy required.

- Moderate: Mild to moderate limitation in activity of the subject; no or minimal medical intervention/therapy required.

- Severe: Marked limitation in activity of the subject, some assistance usually required; medical intervention/therapy required including possible hospitalization.

Serious adverse events are defined as those which result in death, hospitalization, persistent or significant incapacity or substantial disruption of the ability to conduct normal life functions (aka disability), or congenital anomaly / birth defect.

Previously reported treatment-emergent adverse effects are described further in the risks section below.

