## **Withdrawal of Subjects**

Patients may withdraw at any time at their discretion. Subject withdrawn from and/or terminated from research with or without their consent are those who are found to not meet inclusion/exclusion criteria, and/or are not able to complete the research protocol in its entirety, as well as those who suffer a treatment-emergent adverse effect requiring medication discontinuation. For any subjects who withdraw from research, including partial withdrawal from procedures, study data of the withdrawn subject will not be included in statistical analysis and will be shredded.

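### The discontinuation rule has no severity threshold, no count and no clear scope: read literally, mild expected drug effects could end the trial; read per subject, it widens who can be withdrawn and lose their data

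*Combined protocol and SAP*

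**What the plan says.** The rule is the first item in the list of measures that closes Risks to Subjects (section 6): "Study will be discontinued if subjects experience any negative effect from the medication". Nothing there or elsewhere adds a grade, a count, a rate or a person who decides.

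Other sections bear on it:

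- Adverse Events and Serious Adverse Events grades events from "Mild: Transient or mild discomfort (<48 hours) to the subject; no medical intervention/therapy required" up to "Severe: Marked limitation in activity of the subject, some assistance usually required", and defines serious events separately. It ties none of these to stopping.
- Risks to Subjects anticipates a drug effect: "Subjects may have mild ptosis in due to botulinum eye drop but it will eventually improve". It then adds that "the drop can be used in the opposite eye to give symmetry".
- Procedures Involved (section 5) lets the PI unblind and treat an individual patient whose side effects need it. It also sets up the lead-in: "we will do the study with BT eye drops on first 10 patients and then evaluate the results".
- The later Procedures Involved section describes a single application: "the examiner will apply botulinum eye drops or saline to the one of the subject's eyes".
- Withdrawal of Subjects has its own trigger, which covers "those who suffer a treatment-emergent adverse effect requiring medication discontinuation". Data from withdrawn subjects are left out of the analysis and shredded.

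**The concern.** The sentence is an operative safety commitment, so an investigator who sees one case of mild ptosis has to decide what it requires. The text allows two answers, and each causes a problem.

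If the whole study stops, an expected and reversible effect can end the trial before its question is answered, perhaps before anyone has been randomised.

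If only the subject stops, the trigger is wider than the one in Withdrawal of Subjects. Because the drop is given once, there is seldom any medication left to discontinue, so that section's own trigger would rarely apply. The bullet in section 6 would then decide in practice who leaves because of side effects. If leaving means withdrawal, the data go too. Ptosis is a lowering of the lid, and the primary outcome is palpebral fissure height. Removing BT patients because they developed ptosis would therefore remove patients with lower lids after treatment.

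**Working it through.** **1. Does any section limit the rule?** The grading scale could supply a threshold, but the rule does not refer to it. The withdrawal section could supply the scope, but neither text refers to the other. A drug-related event of the mild grade falls within the words of the rule.

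**2. Do other sections assume the trial continues?** Yes. Individual unblinding and treatment, event monitoring throughout the study, subject-level withdrawal, and the expectation that mild ptosis will resolve all presuppose a trial that is still running.

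**3. Literal reading: chance of at least one trigger.** The documents give no event rate, and section 6 says that no studies have evaluated topical BT ophthalmic solution. The per-subject rate p of drug-related effects is therefore an assumption, and one event is taken as sufficient. The number of BT exposures n is 10 (lead-in), 17 (one BT arm), or 10 + 17 = 27 if the lead-in patients are additional to the 34, which the plan leaves unclear.

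Chance = 1 − (1 − p)^n. For example, with p = 0.05 and n = 10: 1 − 0.95^10 = 0.401.

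| Assumed p | n = 10 | n = 17 | n = 27 |
|---|---|---|---|
| 2% | 18% | 29% | 42% |
| 5% | 40% | 58% | 75% |
| 10% | 65% | 83% | 94% |
| 20% | 89% | 98% | 99.8% |

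The chance passes one half at p = 1 − 0.5^(1/n), which is 6.7%, 4.0% and 2.5% for n = 10, 17 and 27.

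**4. Per-subject reading: shift in the BT mean.** Assume 17 BT patients with normally distributed changes in fissure height (SD 1), of whom k are removed and their data dropped.

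*Upper bound: those removed are exactly the largest responders.* The mean response falls by the sum of the k largest expected order statistics divided by 17 − k. For a sample of 17 these are 1.794, 1.319 and 1.029.

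- k = 1: 1.794/16 = 0.11 SD
- k = 2: 3.113/15 = 0.21 SD
- k = 3: 4.142/14 = 0.30 SD

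*Removal by lowest final lid height.* If baseline is independent of change and its SD is r times the SD of change, the correlation between response and final height has size 1/√(1 + r²), and each shift is multiplied by it.

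| r (assumed) | Factor | k = 1 | k = 2 | k = 3 |
|---|---|---|---|---|
| 1 | 0.707 | 0.08 | 0.15 | 0.21 |
| 2 | 0.447 | 0.05 | 0.09 | 0.13 |
| 3 | 0.316 | 0.04 | 0.07 | 0.09 |

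*Removal unrelated to response.* The shift is 0.

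The plan gives no effect size or SD for its 17 per group, so these shifts cannot be turned into a share of the planned effect without a further assumption.

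**The case against.** The strongest reply is that the bullet is loosely worded and means the individual subject. The four provisions in step 2 support this, and it is the more likely intent. A reader might infer from the literal words that the sponsor plans to close the trial at the first mild event. The documents as a whole do not support that. The word for subjects is plural, which leaves some room to require more than one event, though no number is given. Discomfort from instilling the drop is listed separately, under psychosocial risks, so transient discomfort is not automatically an effect of the medication.

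A reader might also infer that the rule itself discards data. It does not. The loss comes from Withdrawal of Subjects, and only if discontinued means withdrawn. Correcting that section alone would remove the bias. Under blinding, saline patients with complaints could also be discontinued, and for effects such as redness or pain the direction of any bias is not established.

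Finally, every rate in the working is assumed, and a strict rule can be defended as precaution for an unstudied route.

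All of this stands, and it narrows the point. It does not remove it: the words say study, no section corrects them, and the per-subject reading still sets a wider trigger than the withdrawal section. A rule that trivial events can trigger and that can be read in two ways is not dependable protection.

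**Conclusion.** The point holds as a defect in a stated rule, and the rule should be changed. The missing threshold and unclear scope are plain from the text. Under the literal reading, mild, expected and reversible effects can end the trial, possibly in the all-BT lead-in, contrary to what the other sections assume. Under the likelier per-subject reading, more patients become liable to removal. If that means withdrawal, dropping BT patients with ptosis biases the fissure-height effect toward zero.

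The size cannot be established from the documents. The stopping chances of 18% to 99.8% depend on assumed rates of 2% to 20% and on one event being enough. The shifts of 0 to 0.30 SD depend on how many patients are removed, how removal relates to response, and ptosis being counted as a negative effect. These figures show the mechanisms and are not forecasts; the bias may be small. Adverse events would still be monitored and reported on either reading.

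**What to change.** Replace the bullet in Risks to Subjects with a study-level pause and IRB review, triggered by a drug-related event that meets the severe grade or the serious-event definition already in the protocol. The IRB may add a cluster of moderate events as a further trigger.

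State that a subject with any lesser adverse effect is treated, reported, kept in scheduled follow-up to 3 months, and kept in the efficacy and safety analyses unless consent is withdrawn. Amend Withdrawal of Subjects so that these subjects' data are neither excluded nor shredded. Leave the opposite-eye drop to the investigator's judgement; barring it would take away the symmetry measure that section 6 mentions directly after ptosis.

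The cost is an IRB wording amendment to two sections, with no extra patients, visits or procedures. The downside is a stopping rule less strict than the present literal wording, for a route that has not been studied. The severity-based pause offsets this.
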